3.1.2. Rationale for study design

A single cohort study was chosen to estimate the incidence of dengue in the community. Data will be collected from a population of individuals aged 6 months and older for maximum four dengue seasons. Inclusion of individuals of various ages will further allow for a better understanding of disease dynamics, clinical spectrum, and validate attack rates for potential subgroups to be included in future dengue vaccine trials.

This study will use cluster (household) sampling to take into account the correlation that may exist within households. Individuals within a household are expected to have a more similar risk of infection compared to individuals from different households. For example, individuals living in the same household are more likely to share similar risk of being exposed to DENV infected mosquitoes. The sample size has been adjusted to account for this between-cluster variability.

A possible bias *may arise from the* non-response rate. *To reduce the possibility of this potential bias, visits will be scheduled* on weekends or at times *more convenient to the subject*. Where applicable, FHP community health care workers will facilitate communication between study staff and participants.

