8.2.2. Estimating design effect and precision

The normal approximation of the Poisson distribution was used for calculating 95% CI for this cluster design. The variance was adjusted for a design effect of 1.8 to account for the between-cluster variability.

The design effect measures the increase in the standard error of the estimate due to the sampling design used and is given by: $D = 1 + (b - 1) \rho$, where ρ is the rate of homogeneity (a measure of variability and equivalent to the “intra-cluster correlation”) and b is the average number of subjects sampled per household. Here we assumed b to be 3. Although in theory ρ can have a value up to 1, in practice values higher than 0.4 are uncommon. We used a conservative estimate of 0.4 for this study (Bennett, 1991). The design effect is then estimated to 1.8.

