8.2.3. Expected precision of incidence rate estimates

Table 15 shows the 95% CI for a range of expected incidences based on the Poisson distribution (exact method, normal approximation and the normal approximation accounting for a design effect of 1.8) in different scenarios. The scenarios were defined according to the following criteria:

- Number of subjects enrolled at the beginning of the study (for some sites it will be the second year). At season level and for all sites: 2000, 4000, 1800, 3600, 1500, 3000. For all seasons and for all sites: 4000, 3600 and 3000. At season level and site level: 600 and 500.
- Number of years of follow-up. At study level: 1 or 4 years, but half of the sites will be followed for 3 years and this is taken into account for the calculations. At site level: 1, 3 or 4 years.
- Overall incidences: 3, 6, 9, 12 or 15 events per 1000 person-years.

With an overall sample size of a minimum of about 3,600 subjects enrolled and a follow-up period of one year, the 95% confidence interval (CI) for an expected incidence of dengue of 9 cases per 1000 person-years using a cluster design is [4.7 ; 13.3]. With 3600 subjects enrolled, 4 years of follow-up and new enrolments to keep the number of subjects above 3000 at the beginning of each subsequent season, the 95% CI is [6.3 ; 11.7].

CONFIDENTIAL

116606 (EPI-DENGUE-006 BOD BR)
Protocol Amendment 4 Final

Table 15 Precision of the expected incidences of dengue for a single cohort of subjects in Brazil

	Cohort size	Number of years	Number of person-years	Number of cases	Incidence of dengue (per 1000 person-years)	95% CI of incidence rate (n / 1000 P-Y)						New enrolment		
						Exact (Poisson)		Normal approx		Normal approx with design effect		After Y1	After Y2	After Y3
						Lower	Upper	Lower	Upper	Lower	Upper			
Overall	2000	1	1845.9	6	3.0	1.0	6.7	0.5	5.5	-0.4	6.4			
	2000	1	1845.9	11	6.0	3.0	10.7	2.5	9.5	1.3	10.7			
	2000	1	1845.9	17	9.0	5.2	14.5	4.7	13.3	3.2	14.8			
	2000	1	1845.9	22	12.0	7.5	18.1	7.0	17.0	5.3	18.7			
	2000	1	1845.9	28	15.0	9.9	21.7	9.4	20.6	7.5	22.5			
	4000	1	3691.9	11	3.0	1.5	5.4	1.2	4.8	0.6	5.4			
	4000	1	3691.9	22	6.0	3.8	9.1	3.5	8.5	2.6	9.4			
	4000	1	3691.9	33	9.0	6.2	12.6	5.9	12.1	4.9	13.1			
	4000	1	3691.9	44	12.0	8.7	16.1	8.5	15.5	7.3	16.7			
	4000	1	3691.9	55	15.0	11.3	19.5	11.0	19.0	9.7	20.3			
	4000	4	9086.6	27	3.0	2.0	4.4	1.9	4.1	1.5	4.5			327
	4000	4	9086.6	55	6.0	4.5	7.8	4.4	7.6	3.9	8.1			327
	4000	4	9086.6	82	9.0	7.2	11.2	7.0	11.0	6.4	11.6			327

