Proportion of subjects with secondary symptomatic dengue infection	All symptomatic infection since the previous visit	Total number of IgG positive subjects at the previous visit
Seroprevalence of dengue infection	All dengue IgG positive cases	Total number of subjects tested or previously positive

* Time at risk: In analyses by season the time at risk is calculated as the time from the visit scheduled before the season until the first event during the season, the next scheduled visit or the subject's withdrawal, whichever comes first.

In the analyses of all seasons combined the time at risk is calculated as the time from enrolment until the first event, the end of the study or the subject's withdrawal, whichever comes first.

CIs for incidence rates and proportions will account for clustering of observations within households for the analyses by centre and also the stratification by centres for the overall analyses. Details of the methods will be described in the SAP.

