7. STATISTICAL ANALYSES

Note that data derivation rules are described in Section 11 and will not be repeated below.

Continuous variables will be summarized with number of non-missing observations, mean, standard deviation (SD), median, minimum, maximum, 25th and 75th percentiles. Categorical variables will be summarized with frequency tables; numbers and percentages for each level will be given.

If an elimination code 900 is attributed, then all the analyses planned to be done on the Total cohort will be done on the Total cohort without subjects with code 900, except Template 5 from EPI-DENGUE-006 BOD BR (116606) TFL (Final analysis) (14-JUN-2019) DRAFT.

The final analysis will be performed on the following study sites using data up to the specified study visits and dengue seasons covered up to study termination:

Region/Study sites name	Initial / Expansion / Replacement cohort	Subject numbers	Study visits covered up to study termination	Dengue season covered up to study termination
Rio	Initial	P - PP	Visit 1 to Visit 6	2015, 2016, 2017, 2018
	Replacement*	PP - PP	Visit 1 to Visit 4	2016, 2017, 2018
Manaus	Initial	PPD - PPD	Visit 1 to Visit 6	2015, 2016, 2017, 2018
	Replacement*	PPD - PPD	Visit 1 to Visit 2	2018
Salvador	Initial	PPD - PPD	Visit 1 to Visit 5	2016, 2017, 2018
Natal	Expansion	PPD - PPD	Visit 1 to Visit 3	2017, 2018
Campinas	Expansion	PPD - PPD	Visit 1 to Visit 2	2018

*only 1 replacement cohort

The following results will be available at the scheduled visits for the following tests:

- Dengue IgG ELISA will be available at Visit 1
- For Visit 2 onwards, Dengue IgG ELISA will be available for subjects with IgG negative at the previous visit.

The following results will be available in case of SDC, for the following tests:

Assays	Result type	Early presenters		Late presenters	
		Acute sample (first visit)	Convalescent sample (follow-up visit)	Acute sample (first visit)	Convalescent sample (follow-up visit)
RT-qPCR	Positive, negative or not typeable DENV type Copies/ml Final classification into positive or negative (used for the dengue case classification)	Yes	TNP	TNP	TNP
NS1 ELISA	Reactive or no reactive	Yes	TNP	Yes	TNP
Dengue IgM ELISA	Reactive or no reactive	Yes	Yes	Yes	Yes
Dengue capture IgG ELISA	Reactive or no reactive	TNP	Yes	Yes	Yes
Hematology / Biochemistry	Numerical results	Yes	TNP	Yes	TNP

TNP = test not performed on the sample as per protocol

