7.2.2. Additional considerations

7.2.2.1. Incidence rate

In light of the low number of dengue episodes, the large number of positive anti-dengue IgG at visit 1 and the number of dengue cases reported outside the season,

1. The analyses of PCR confirmed cases (only 10 cases) and the analyses of secondary dengue infections were removed.
2. The analyses by seroprevalence at each visit were removed,
3. The analyses by season were removed. Only the analyses by calendar year are to be conducted

- 4. Subjects without seroprevalence status at visit 1 were removed from the ATP cohort because serological status of symptomatic/inapparent dengue infections cannot be assessed properly for such subjects
- 5. Planned analyses of medical and vaccination history were removed.
- 6. The statistical method was updated to ignore the household cluster effect and to provide incidence rate with confidence interval in absence of dengue episodes in a calendar year for a study site .

Regarding the last point, the expected annual incidence rate for a cohort of subjects followed over a full calendar will be computed using a log-linear model with the number of dengue events (all cases) as depend variable and the total number of subject-month as offset. The model will include the study site, year and month as independent categorical fixed effects (see below).

The expected annual incidence rate in a study site for each year will be estimated as the average of incidence rate over months

```

proc genmod ;
  class center month year;
  model evt= center year month /
    dist=poisson link=log offset=ln TYPE3;

  ods output Estimates=estimc;
  estimate 'center PPD 2014' intercept 12 center 12 0 0 0 0
    year 12 0 0 0 0
    Month 1 1 1 1 1 1 1 1 1 1 1;
  estimate 'center PPD 2014' intercept 12 center 0 12 0 0 0
    year 12 0 0 0 0
    Month 1 1 1 1 1 1 1 1 1 1 1;
  estimate 'center PPD 2014' intercept 12 center 0 0 12 0 0
    year 12 0 0 0 0
    Month 1 1 1 1 1 1 1 1 1 1 1;
  estimate 'center PPD 2014' intercept 12 center 0 0 0 12 0
    year 12 0 0 0 0
    Month 1 1 1 1 1 1 1 1 1 1 1;
  estimate 'center PPD 2014' intercept 12 center 0 0 0 0 12
    year 12 0 0 0 0
    Month 1 1 1 1 1 1 1 1 1 1 1;
  estimate 'overall 2014' intercept 12 center 2.4 2.4 2.4 2.4 2.4
    y 12 0 0 0 0
    Month 1 1 1 1 1 1 1 1 1 1 1;
  estimate 'center PPD 2015' intercept 12 center 12 0 0 0 0
    year 0 12 0 0 0
    Month 1 1 1 1 1 1 1 1 1 1 1;
  estimate 'center PPD 2015' intercept 12 center 0 12 0 0 0

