```

```

estimate 'overall' intercept 60 center 12 12 12 12 12
                        year 12 12 12 12 12
                        Month 5 5 5 5 5 5 5 5 5 5 5 5;
estimate 'overall center PPD' ' intercept 60 center 60 0 0 0 0
                        year 12 12 12 12 12
                        Month 5 5 5 5 5 5 5 5 5 5 5 5;
estimate 'overall center PPD' ' intercept 60 center 0 60 0 0 0
                        year 12 12 12 12 12
                        Month 5 5 5 5 5 5 5 5 5 5 5 5;
estimate 'overall center PPD' ' intercept 60 center 0 0 60 0 0
                        year 12 12 12 12 12
                        Month 5 5 5 5 5 5 5 5 5 5 5 5;
estimate 'overall center PPD' ' intercept 60 center 0 0 0 60 0
                        year 12 12 12 12 12
                        Month 5 5 5 5 5 5 5 5 5 5 5 5;
estimate 'overall center PPD' ' intercept 60 center 0 0 0 0 60
                        year 12 12 12 12 12
                        Month 5 5 5 5 5 5 5 5 5 5 5 5;

run;
    
```

```

data estimc; set estimc;
    if label='overall' or index(label,'overall center') then do;
        estimate=exp(lbetaestimate/60);
        lower=exp(lbetalowercl/60);
        upper=exp(lbetauppercl/60);
        end;
    else do;
        estimate=exp(lbetaestimate/12);
        lower=exp(lbetalowercl/12);
        upper=exp(lbetauppercl/12);
        end;
run;
    
```

In case of subgroup analysis by gender or by age at visit 1 (<=17years, 18-49 years and >= 50years) or in case the model does not allow estimating confidence interval (eg problem of convergence or situation where there is no event in a site, in a calendar year or in a month) CI will be computed using exact CI based on a Poisson Distribution.

The following case provides the SAS code for the exact CI for incidence rate per subject-year when there are 14 events and 400 subject-years:

```

data check;
    fu=400;
    n=14;
    Rate=n/fu;
    LL_rate= GAMINV(0.025, n)/fu;
    UL_rate= GAMINV(0.975, (n+1))/fu;
    LL_rate_=cINV(0.025, 2*n)/(2*fu);
    UL_rate_=cINV(0.975, 2*n+2)/(2*fu);
    
```

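### SAP Amendment 1 drops the promised household-cluster adjustment for incidence CIs, which are then too narrow if enrolled housemates' risk is materially correlated

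*SAP*

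**What the plan says.** Households are the sampling unit, and all members of a selected household are invited (Protocol 8.2.1). Protocol 3.1.2 gives the reason for expecting correlation: "Individuals within a household are expected to have a more similar risk of infection compared to individuals from different households". Protocol 8.5.2 then commits: "CIs for incidence rates and proportions will account for clustering of observations within households for the analyses by centre". For planning, Protocol 8.2.2 assumes three subjects per household and says of the intra-household correlation: "We used a conservative estimate of 0.4 for this study". The resulting DE of 1.8 is built into the precision statement in 8.2.3, whose four-year result reads "the 95% CI is [6.3 ; 11.7" per 1000 person-years.

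SAP Amendment 1 (29 October 2019) changes this in 7.2.2.1 item 6, repeated in section 1: "The statistical method was updated to ignore the household cluster effect". The main method is now PROC GENMOD with a Poisson distribution and fixed effects for site, year and month. It has no REPEATED statement and no SCALE option. For gender and age subgroups, and wherever the model gives no interval, "CI will be computed using exact CI based on a Poisson Distribution".

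The lead-in to the list of changes begins "In light of the low number of dengue episodes" and also cites the many IgG-positive subjects at Visit 1 and cases outside the season. Item 6 adds the aim of an interval for site-years without cases.

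DE, ICC and GEE remain in Amendment 1's abbreviation list, but no analysis section uses them. Section 7.1.2 still tabulates subjects per household. Section 8 says that all analyses are descriptive.

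**The concern.** Neither Poisson method contains a household term. Site fixed effects absorb differences between sites, but not the tendency of cases to occur together in one home. If that tendency is material and more than one housemate is enrolled, the variance of the case count exceeds the Poisson variance and the stated 95% intervals cover less than 95%.

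In a purely descriptive study the CI is the only statement of uncertainty around the primary incidence estimate. The protocol quoted its precision with the DE included, so an interval computed without it will look tighter than planned. Nothing in the SAP text would tell the reader whether that gain is real. Subjects per household show the cluster size but not the correlation.

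The reasons given do not establish independence. Few events make a DE imprecise; they do not make it 1. Wanting an interval for site-years without cases is reasonable, but does not require ignoring households in the overall, yearly and larger site rates.

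**Working it through.** **Inputs.** Subjects per household b = 3, correlation rho = 0.4 and DE 1.8 (Protocol 8.2.2). Incidence 9 per 1000, with 3322.7 person-years (3600 subjects, one year) and 8611.3 person-years (3600 subjects, four years) (Protocol 8.2.3, Table 15).

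**Reproducing the plan's figures.**
- DE = 1 + (b − 1) × rho = 1 + 2 × 0.4 = 1.8.
- Half-width without DE = 1.96 × 1000 × √(0.009 / person-years).
- 8611.3 person-years: half-width 2.00, giving [7.0; 11.0]. Multiplied by √1.8 = 1.342 it is 2.69, giving [6.3; 11.7]. Both match Table 15.
- 3322.7 person-years: [5.8; 12.2] without and [4.7; 13.3] with the DE. Both match.

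**Effect of omitting the DE.** Nominal coverage of an unadjusted interval is 2Φ(1.96/√DE) − 1. The adjusted interval is √DE times as wide.

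| DE | Coverage if ignored | Adjusted / unadjusted width |
|---|---|---|
| 1.0 | 95.0% | 1.00 |
| 1.1 | 93.8% | 1.05 |
| 1.2 | 92.6% | 1.10 |
| 1.4 | 90.2% | 1.18 |
| 1.8 | 85.6% | 1.34 |

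With b = 1 the DE is 1 whatever rho is. With b = 2, rho = 0.1 gives DE 1.1 and rho = 0.2 gives DE 1.2.

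**The SAP's exact Poisson CI by simulation.** Assumed: households of three, beta-binomial within household, 20,000 runs per setting.

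| Expected events | rho ≈ 0 | 0.1 | 0.2 | 0.4 |
|---|---|---|---|---|
| about 77 | 95.5% | 93.2% | 91.0% | 86.2% |
| about 32 | 95.6% | 93.8% | 91.5% | 86.3% |
| about 9 | 95.7% | 93.8% | 91.4% | 86.4% |
| about 5 | 97.5% | 96.0% | 94.4% | 90.9% |

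Exact limits are conservative at very low counts, which offsets part of the shortfall near five events. By nine events the offset has mostly gone. Gender subgroups split households: at rho 0.4 and b = 3 their DE is 1.27 (two/one split) to 1.40 (random split), against 1.8 overall.

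**Would a household-robust interval work with few events?** The final analysis runs "using data up to the specified study visits and dengue seasons covered up to study termination". Section 7 lists 4 + 4 + 3 + 2 + 1 = 14 site-seasons for the five sites. Assuming 500 subjects per site and one year each gives 7000 person-years, so 63 events at 9 per 1000 or 42 at 6 per 1000. The true number of laboratory-confirmed cases is not in the documents. For the overall rate, with households of three and rho from 0.05 to 0.4, a household-robust CI covered 94.6% to 95.2% at both event counts.

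**The case against.** The protocol leaves CI details to the SAP and allows changes that are described and justified. Amendment 1 states this one in section 1 and 7.2.2.1 and points to both from section 10. No test or threshold depends on the interval. The correlation of 0.4 is one the protocol itself calls conservative: at 9 per 1000 it means that, given one case, each housemate has a probability of 0.009 + 0.4 × 0.991 = 0.405 of being a case in the same period. At rho 0.1 the loss of coverage is one to two percentage points. Four of the five sites found interested subjects through community contact (SAP 2.2.3), so b = 3 is uncertain. A DE resting on few multi-case households is itself imprecise.

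Most of this stands. It limits the size of the problem and argues against an elaborate remedy. It does not make an independence-based interval valid, and nothing in the SAP text shows that the DE is close to 1.

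Some stronger readings are not supported:
- **A hidden change or internal contradiction.** Section 7.2.1 repeats the clustering sentence only as the protocol's plan; the departure is declared.
- **Intervals that are in fact 34% too narrow.** That is the planning value; the realised DE is unknown.
- **No DE reported anywhere.** This can be said only of the SAP text, since the table template is a separate file.
- **A fully adequate method in the superseded SAP of June 2019.** Its cluster-based variance applied to ten or more events. Below ten, its Pearson scale had no household term.

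**Conclusion.** The point holds conditionally and is worth fixing. Amendment 1 removes a protocol commitment on the interval for the primary estimate, without evidence in its text that household correlation is negligible. The intervals are too narrow if, and only if, more than one subject per household is enrolled and their risk is materially correlated. The loss runs from about one percentage point of coverage at DE 1.1 to about nine at DE 1.8 (95% to 85.6%), the latter at a deliberately cautious planning value.

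The shortfall is clearest for the pooled rate. It is small in cells with about five events unless the correlation is high, while cells approaching ten events behave much like the pooled rate. Crude point estimates are not affected. The coverage figures rest on assumed household size, correlation and event counts, because the documents report none of the realised values.

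**What to change.** Amend item 6 in 7.2.2.1 and in section 1; leave 7.2.1 as the record of the protocol plan.

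1. Report the overall incidence rate, and yearly and site rates with 10 or more events, with a household-robust 95% CI. Use a Poisson model on subject-level records with REPEATED SUBJECT = household within site and an independence working correlation, which leaves the point estimate unchanged; or use a household bootstrap.
2. Report the observed overall DE and the number of households with more than one case.
3. Keep the plain exact Poisson CI for cells with fewer than 10 events and for the gender and age subgroups. Add a footnote that these intervals assume independence within households and should be read alongside the observed DE.

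The cost is SAP wording and a small programming change: household numbers are already assigned (Protocol 5.2). If the DE is near 1, the intervals barely move and the simplification is borne out. Otherwise the larger rates get wider intervals, by about 5% to 18% at DE 1.1 to 1.4 and 34% at 1.8. The DE will be imprecise when few households have more than one case: in the 42-event illustration with a true DE of 1.2, 90% of estimates fell between 1.01 and 1.40. The change does not address the recruitment of interested subjects at four sites, nor how the ESTIMATE statements average monthly rates, which is a separate question.

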2.4. Dengue seasons

Dengue season:

Region/study site name (site number)	Dengue season
Rio (PPD)	1st January to 30th June
Manaus (PPD)	1st January to 30th June
Salvador (PPD)	1st January to 30th June
Natal (PPD)	1st January to 30th June
Campinas (PPD)	1st January to 30th June

3. OBJECTIVES**3.1. Primary objective**

- To estimate the incidence of laboratory-confirmed symptomatic dengue infection in the study population by year/season.

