3.2. Secondary objectives

- To estimate the serotype-specific incidence of virologically-confirmed symptomatic dengue infection in the study population overall and by season.
- To estimate the incidence of symptomatic dengue infection (including laboratory-confirmed and probable cases) in the study population by study site, gender, age-group, previous dengue exposure (primary or secondary), overall and by season.
- To estimate the prevalence of previous dengue infection (dengue seroprevalence) in the study population overall and by study site, gender and age-group at enrolment.
- To estimate the incidence of primary inapparent dengue infection, in the study population overall and by study site, gender age-group and by season.
- To describe symptoms and spectrum of dengue disease in the study population.

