11. DATA DERIVATION RULES AND STATISTICAL METHODS

11.1. Data presentation

The following decimal description will be used for the analyses:

Display Table	Parameters	Number of decimal digits
Dengue cases	Incidence rate (in 1000 person-years) with LL & UL, person-years	1
Dengue cases	% of count, including LL & UL of CI	1
Dengue cases	Minimum, maximum, range	Number of decimals in the raw data
Dengue cases	Mean, median	Number of decimals in the raw data +1
Dengue cases	SD	Number of decimals in the raw data +2
Hematology/biochemistry	%	1
Demographic/baseline characteristics and changes between scheduled visits	Percentage, mean, median, standard deviation, minimum, maximum, Q1, Q3	1

CI = confidence interval

LL = lower limit of the confidence interval

SD = standard deviation

UL = upper limit of the confidence interval

Q1/Q3 = 25th and 75th percentiles

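### The incidence model is asked for a rate and interval in all 25 site-years of 2014 to 2018, but at least 6 have no person-time and no visible rule suppresses or flags them

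*SAP*

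**What the plan says.** SAP Amendment 1, section 7.2.2.1, models events by log-linear Poisson regression with subject-months as offset. One stated purpose of the change in method is "to provide incidence rate with confidence interval in absence of dengue episodes in a calendar year for a study site". On structure it says: "The model will include the study site, year and month as independent categorical fixed effects". No site-by-year interaction appears in the text or in the MODEL statement. The code then contains:

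- one ESTIMATE statement per site and calendar year, 2014 to 2018;
- one `overall` statement per year, averaging all five sites;
- one `overall center` statement per site, averaging all five years;
- one grand `overall` statement.

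An exact Poisson interval replaces the model for gender and age subgroups, or when the model cannot give an interval; the examples are "eg problem of convergence or situation where there is no event in a site, in a calendar year or in a month". The purpose and the examples concern absent events. Neither mentions absent follow-up, and section 11.2 provides no handling of missing data.

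Section 7 says the final analysis covers the listed sites "using data up to the specified study visits and dengue seasons covered up to study termination". In the table below that text, the first covered season is 2015 at Rio and Manaus, 2016 at Salvador, 2017 at Natal and 2018 at Campinas. Section 2.4 dates the season at every site "1st January to 30th June".

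**The concern.** A site that has not opened has neither cases nor person-time, so it has no observed incidence. A table that prints a rate and 95% interval for Campinas in 2014, in the same format as Rio in 2016, invites the reader to take it as a measurement. In fact the number would be Campinas's later level multiplied by a year pattern learned elsewhere. Protocol section 1.2 expects some sites to have high transmission and others limited transmission. A common year pattern is therefore a substantive assumption, and it cannot be checked in cells without data. The interval does not reflect it either.

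The study is meant to support attack-rate assumptions for later efficacy trials, so users of the results need to tell observed site-years from predicted ones. The same predicted values also enter the averages over years and over sites.

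**Working it through.** The plan states no count of empty site-years, so it has to be derived.

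**1. Rows requested.** 5 sites × 5 years = 25.

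**2. Rows without person-time.** Seasons run from January to June. If a site's first covered season is in year Y, its follow-up began no earlier than calendar year Y − 1.

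- Salvador, Y = 2016: 2014 is empty (1).
- Natal, Y = 2017: 2014 and 2015 are empty (2).
- Campinas, Y = 2018: 2014, 2015 and 2016 are empty (3).

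The minimum is 1 + 2 + 3 = 6 of 25 (24%). If follow-up at these sites began only within the first covered year, Salvador 2015, Natal 2016 and Campinas 2017 are empty too: 9 of 25 (36%). Rio and Manaus are taken to have 2014 data: the rationale of Protocol Amendment 3 (9 January 2015) says the first two sites had completed enrolment, and the interim SAP, section 10.1, names them as Rio and Manaus.

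**3. Cross-check by visits.** Section 2.1 ends the study at the visit after the 2018 season. Counting back from July to December 2018 by Protocol Tables 5 and 6 (36 months at Salvador, 24 at Natal, 12 at Campinas) puts enrolment in about July to December of 2015, 2016 and 2017. With every 28-day window used, the earliest dates are March 2015, May 2016 and June 2017. The minimum is again six, and nine looks less likely.

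**4. What the model returns.** The log rate is α + site + year + mean of the 12 month effects, with 1 + 4 + 4 + 11 = 20 parameters. With staggered entry the design has rank 20 of 20, and all six empty rows are estimable. This reads `y` as `year` and takes 12 month coefficients per row. As extracted, the 2014 rows and the 2015 rows for the first four sites show 11; that may come from the PDF, but a row with intercept 12 and 11 month coefficients is not estimable.

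One simulated data set illustrates the mechanism. Its inputs are assumptions: 530 subjects per site, 12 per 1000 person-years, January to June three times the rate of July to December, entry in August 2014 (Rio), October 2014 (Manaus) and September 2015, 2016 and 2017 (the later sites), follow-up to September 2018. Campinas 2014, with zero follow-up, was given 31.8 (7.9 to 128.3) per 1000 person-years. That is the Campinas 2018 fit multiplied by Rio's 2014-to-2018 ratio: 18.52 × 13.31 / 7.74 = 31.85, equal to the fitted 31.83 apart from rounding. Nothing observed at Campinas in 2014 enters it.

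**5. What the fallback returns.** The exact formula reproduces Protocol Table 15 for 30 cases in 3322.7 person-years (6.1 to 12.9 per 1000). With no events and no follow-up, the rate is 0/0, the upper limit divides by zero, and the lower-limit quantile with zero events is undefined.

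**6. Weight of unobserved site-years in the averages (log scale).** Each site has 2.4/12 = 20% of a yearly `overall` row. Each year has 12/60 = 20% of an `overall center` row.

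| Row | 6 empty | 9 empty |
|---|---|---|
| `overall 2014` | 60% | 60% |
| `overall 2015` | 40% | 60% |
| `overall 2016` | 20% | 40% |
| `overall 2017` | 0% | 20% |
| `overall center`, Salvador | 20% | 40% |
| `overall center`, Natal | 40% | 60% |
| `overall center`, Campinas | 60% | 80% |

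The `overall center` rows for Rio and Manaus carry none.

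**7. Related code points.** Three ESTIMATE statements (`overall 2014`, `overall 2016` and the fourth site in 2018) name an effect `y` that is not in the model. The text also leaves open whether the fallback replaces the whole table or only the affected rows.

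**The case against.** The best defence is that prediction is the declared target: section 7.2.2.1 estimates the expected rate for a cohort followed through a full calendar year, because events were few. All analyses are descriptive (section 8). The coverage table is in the SAP, and section 11.1 lists "Incidence rate (in 1000 person-years) with LL & UL, person-years" among the displayed items, so a zero may be visible. The separate table shells could contain a display rule. The fallback gives no number at all for these rows, so it cannot mislead.

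Much of this is fair. It does not fully answer the point. In a partly followed site-year, the model fills missing months around data from that site and year; in an empty one there is nothing to fill around. Listing person-years is not an instruction to suppress a row, and it would not show how much of a pooled row is unobserved.

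Three stronger readings are tempting, and the documents support none of them:

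- *The overall rows are invalid.* Equal weights over five sites are a legitimate standardisation. What is missing is a statement of which sites were under observation.
- *The primary result is compromised.* The primary objective is "To estimate the incidence of laboratory-confirmed symptomatic dengue infection in the study population by year/season", but the model's outcome is described as all cases, and no text ties these overall rows to the laboratory-confirmed endpoint. The site breakdown is secondary: "in the study population by study site, gender, age-group, previous dengue exposure (primary or secondary), overall and by season".
- *The intervals badly understate uncertainty.* That depends on site-by-year variation and event numbers that the documents do not give; the only count is 10 PCR-confirmed cases. In the illustration the empty row already has a much wider interval than a followed one (Campinas 2014, 7.9 to 128.3; Campinas 2018, 10.5 to 32.7).

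**Conclusion.** The point holds as a gap in specification that affects what is reported. Of the 25 site-year rows requested, at least 6 and at most 9 have no person-time. The model would fill them by assumption, the fallback cannot compute them, and the visible text has no rule for either case. The five-year rows for Salvador, Natal and Campinas are affected most, because they are presented as a site's own average while including years before the site opened. The yearly overall rows need disclosure rather than a different estimator.

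This rests on the section 7 coverage table, on the common season dates, on Rio and Manaus having 2014 follow-up, and on code read with `year` for `y` and 12 month coefficients. Enrolment dates are not given, hence the range. The table shells were not available. No claim is made about how far any reported rate would be wrong.

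**What to change.** 1. Report a site-year rate only where actual person-time is above zero. Print *not observed* otherwise, under both the model and the fallback, and show person-years beside each rate.
2. Build each `overall center` contrast and its divisor from the calendar years in which that site has actual person-time. Do not hard-code the number of months, because enrolment dates decide whether the year before the first covered season counts. Alternatively, label the row as a prediction that includes unobserved years.
3. Keep equal site weights in the `overall` rows if wanted, with a footnote naming the sites under observation in each year.
4. State whether the exact Poisson fallback replaces the whole table or only the affected rows.
5. Correct `y` to `year` in the three ESTIMATE statements, and check that every row has 12 month coefficients.

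The cost is SAP wording, a few changed statements and divisors, and footnotes; no new data are needed. The tables will have fewer filled cells.
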